C	May 22, 2019	90702637 Rev/Ver AL	11.4 SICD Implant Visit, Figure 11-1	Completely re-written and new Figure added. Describes the flow of the overall procedure with testing two-electrode configurations (Parallel and 90°)". The new Figure 11-1 describes a new energy test step sequence that starts at 30 J, rather than 50 J, and requires only 2 VF inductions per shock configuration.	New computer modeling data suggests two shock coils inserted at a 90° angle (an "L" configuration) might perform as well as two electrodes inserted in parallel but could result in a more favorable product. The original protocol envisioned this possibility but was not clear about how testing in another configuration should be done. So, changes to the test procedure were needed to allow testing of both configurations. This is the main reason for the protocol revision.

Revision History

Revision version	Protocol Date	Template number and version	Protocol section modified	Summary of changes	Justification for Modification
C	May 22, 2019	90702637 Rev/Ver AL	11.4.2 Temporary Insertion of the Second S-ICD Electrode	Added more specific description of how the 2 nd electrode is inserted in both parallel and 90° configurations	Clarification – to support changes in 11.4 (see above)
C	May 22, 2019	90702637 Rev/Ver AL	11.4.3 Figure 11-1	Clarifications to the DFT testing procedure and stopping rules. The old Figure 11-1, originally shown in section 11.4.3 was removed and a new Figure 11-1 was added to section 11.4 (see above).	Needed to support testing of 2-electrode configuration (Parallel and 90°) per 11.4 above. Current results showed that all subjects were converting at 40 J or lower, so the starting energy was reduced to 30 J and the new testing only require 2 VF inductions per test configuration.
C	May 22, 2019	90702637 Rev/Ver AL	11.4.4 – Allowable Test Sequence Revisions	Added section 11.4.4 to describe the range, and limits, of possible changes that could be made to the test procedure.	Provide clarity about the scope and limits of changes that can be made without need for a new protocol revision.
C	May 22, 2019	90702637 Rev/Ver AL	All sections	Minor changes made throughout the document to support the major changes described above.	Consistency, clarity with the major changes
C	May 22, 2019	90702637 Rev/Ver AL	20.4 Investigator Reporting Requirements	Updated AE reporting	Updated per current Boston Scientific requirement

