	
2 additional VF inductions and shocks per the protocol specified testing sequence. After testing is completed in the first configuration, the second configuration will be tested using 2 additional VF inductions. Lastly, after the DFT testing is completed, the second S-ICD electrode and Investigational S-ICD Y-Adapter are disconnected and removed, and the S-ICD system implant is completed per investigator's usual practice and experience.
 
A schematic representation of the Investigational S-ICD Y-Adapter and the electrode/PG connection during investigational testing is shown below. The second electrode is either parallel to the first with 0.5-2 cm spacing (left figure) or is inserted at an ~90 degree angle from the first (right figure).
 
Planned Number of Subjects	A maximum of 42 subjects will be enrolled to obtain at least 30 complete datasets.
Planned Number of Investigational Sites / Countries	A maximum of 10 sites are allowed in Europe and possibly in the United States.
Primary Safety Data	All S-ICD system and procedure related adverse events

**Acute Feasibility Investigation of a New S-ICD Electrode Arrangement
for Reduction of Defibrillation Energies**

[ASE Study]

Primary Effectiveness Data	Defibrillation Threshold (DFT) of the 2-electrode configuration (Parallel and 90°)
Additional Data	
• VF conversion success for the 2-electrode configurations (Parallel and 90°)• Shock impedance of both the one- and 2-electrode configuration (Parallel and 90°)
Method of Assigning Subjects to Treatment	All enrolled subjects are intended to have the 2 nd electrode inserted and undergo acute testing. The order of 2-electrode configuration (Parallel and 90°) testing will be alternated based on the subject's ID # to help reduce the possibility of a test order bias.
Follow-up Schedule	Study procedures/visits will occur at the following time periods: 
• Consent and enrollment visit• S-ICD implant procedure visit• 90-day follow-up visit (to be conducted in clinic or by telephone at 90±45 days post-implant)
Study Duration	Duration of the study, from the first enrollment to the last subject's final visit is expected to be approximately 20-28 months. Individual subjects will be followed from enrollment until their 90-day follow-up visit.

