4.2.2. Pre-Clinical Testing of an Alternative S-ICD Electrode System

4.3. Safety of Acute VF Conversion Testing

4.3.1. ICD Experience

The implantation of ICD and S-ICD systems has a long history of performing VF conversion testing at the time of system implant. The rationale for such testing is threefold: 1) to ensure appropriate sensing and detection of VF, 2) to obtain evidence of successful VF conversion of the system and, 3) to help ensure a safety margin exists between an energy level known to convert VF and the maximum output of the device.

Available data suggests that VF conversion testing and evaluation of the DFT is safe when conducted by experienced implanters with the right training and backup defibrillation support. There are many published studies that evaluated paired DFT of new shock electrodes⁶⁻⁸, different shock vectors⁹⁻¹¹, and different shock waveforms¹²⁻²⁵. Such testing would typically require 3 to 5 VF inductions and shocks per test configuration to assess the DFT of each test configuration. One large trial of DFT testing was the Low Energy Safety Study (LESS)²⁶, sponsored by Boston Scientific Corporation. Seven hundred and thirty-three (733) subjects underwent extensive VF conversion testing at implant, and a subset of 392 subjects had additional VF conversion testing at pre-discharge, 3 months, and 12 months. Implant testing consisted of the determination the DFT (in which the lowest energy level that succeeds was reconfirmed twice, for a total of 3 tests without failure). This testing typically required 4 to ~14 VF inductions and shocks delivered per subject. Follow-up testing in the Phase 1 subset of 392 subjects consisted of 3 VF inductions and shocks at each of the three follow-up visits, for a total of 9 additional VF conversion tests. Testing was generally well tolerated.

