5.2. Investigational S-ICD Y-Adapter

The Investigational S-ICD Y-Adapter (model 3598) is intended to facilitate ventricular fibrillation (VF) conversion testing of a novel S-ICD subcutaneous electrode configuration.

The Investigational S-ICD Y-Adapter is a sterile, single-use, acute implant accessory. It is intended for short-term use during a testing procedure and must be disconnected at the end of the testing procedure.

For the purpose of the investigational testing for this study, the S-ICD Y-Adapter connects two S-ICD subcutaneous electrodes to an S-ICD pulse generator. It consists of a long tail with an SQ-1 connector pin and a header with two SQ-1 connector ports.

The image consists of several black rectangular blocks of varying sizes. A large, solid black rectangle is centered in the middle of the frame, surrounded by a thin white border. Above this central rectangle is a smaller, solid black rectangle. The background is white, and there are thick black horizontal bars at the top and bottom edges. The overall composition is minimalist and abstract.

5.3. *Required Medical Equipment*

While not specifically part of the study system provided by Boston Scientific, additional equipment provided by the investigational center required for the study include:

- Back-up external defibrillator for emergency rescue
- Continuous blood pressure monitoring
- Fluoroscopic imaging equipment

6. Study Objectives

The primary objective of this acute feasibility study is to assess the defibrillation threshold (DFT) when adding a second left parasternal electrode to an S-ICD system 2-electrode configuration

The secondary objective is to assess the efficacy of 2-electrode configurations (Parallel and 90°) to convert VFJ.

The tertiary objective is to assess factors that influence the DFT when adding the second electrode (e.g. spacing and orientation or angle between electrodes).

7. Study Data

Primary Data:

- All device- and procedure-related adverse events
- The DFTs for the 2-electrode configuration (Parallel and 90°) consisting of two left-parasternal electrodes to left lateral PG

Secondary Data:

- The shock impedance for each of the two S-ICD shock configurations (one parasternal electrode and two parasternal electrodes)
- VF conversion success for the 2-electrode configuration (Parallel and 90°)

8. Study Design

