11.4. S-ICD Implant Visit

The overall flow of the ASE study testing, after the initial S-ICD implant, will follow Figure 11-1. Overall flow of the S-ICD implant and ASE study testing. First, the S-ICD system implant will be started per standard of care. The electrode will be connected to the PG with the Investigational S-ICD Y-Adapter and the single coil configuration tested at 65 J. If the S-ICD system successfully converts VF with 65 J and the safety criteria described in section 11.4.1 are met, the additional investigational testing will proceed. There are two different 2-electrode configurations (Parallel and 90°) that will be tested. The order of testing of 2-electrode configuration (Parallel and 90°) will alternate based on the subject's ID number to help reduce the possibility of a test order bias. Each subject follows only one path in the flow chart of Figure 11-1.

Section 11.4.2 describes how the 2nd electrode is inserted for the parallel and 90° configurations.

Section 11.4.3 describes the how the VF conversion testing is performed. It is expected that testing of each 2-electrode configuration (Parallel and 90°) will require 2 VF inductions and will use the energy test step sequence shown in Figure 11-1. After the first 2-electrode configuration is tested, the 2nd electrode is repositioned, and the VF conversion testing is repeated. Subjects must meet the safety criteria described in 11.4.3 to continue with testing. If any of the safety criteria are not met, the testing will stop. When the additional investigational testing is either completed, or stopped, the 2nd electrode and Investigational S-ICD Y-Adapter will be removed and the S-ICD implant completed per standard of care.

[figure not shown]

Figure 11-1. Overall flow of the S-ICD implant and ASE study testing

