12.1. Study Data

12.1.1. Primary Data and Secondary Data

Primary Data

1. Safety: All device- and procedure-related adverse events through 90 days post-implant procedure.
2. Effectiveness: defibrillation threshold (DFT) of the two-electrode shock configuration - two left-parasternal electrodes to the left lateral PG.

Secondary Data

1. Shock impedance of the electrode conversion tests using both the single electrode (at 65 J) and the 2-electrode configurations (Parallel and 90°).
2. Percentage of defibrillation success of VF conversion at each of the tested energy level

Hypotheses

This is an early-stage feasibility study. There is no formal hypothesis due to study not being powered for its sample size and no control group for comparison. This study seeks to characterize the performance of the new electrode shock configuration by collecting defibrillation conversion and shock impedance data.

Sample Size

This is an early-stage feasibility study and there is no formal sample size calculation. It is estimated that 20 subjects with complete testing, within an electrode configuration, will allow for a reasonable confidence in assessing defibrillation performance. For example, if 19 out of 20 subjects are successfully converted at 50 J (95% success) the resulting 95% confidence interval will be 75.13% to 99.87% using exact test, which is considered acceptable for this early feasibility assessment.

Since some enrolled subjects may not start and/or complete testing due to a variety of reasons, including exceeding the protocol-required safety criteria per Sections 11.4.2 and 11.4.3, and since a protocol revisions was made to add testing of a 2nd 2-electrode configuration (90° configuration), the study will enroll up to 42 subjects so that 30 complete datasets can be expected.

Statistical Methods

This is an early-stage feasibility study to assess performance of the new electrode shock configurations. No specific statistical tests will be performed. Descriptive statistics will be provided as follows,

- Subject demographic and medical history data will be reported as raw numbers and percentage for categorical variables and mean ± standard deviation for continuous variables.
- DFTs and shock impedances will be reported as mean ± standard deviation.
- Defibrillation success at a given energy level (eg 50 J, etc.) will be reported as a percentage and 95% confidence interval.

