27.2. Definitions

Table 26-2: Definitions

Term	Definition
DFT testing (Defibrillation Threshold testing)	Multiple VF conversion tests performed at step-wise energy level to determine the minimum shock energy needed to convert an induced VF episode
VF conversion test	A VF episode is first induced, and a defibrillation shock is then delivered to test whether the shock could convert the VF.
Source document Ref: ISO 14155	Original or certified copy of printed, optical or electronic document containing source data.
Source data Ref: ISO 14155	All information in original records, certified copies of original records of clinical findings, observations, or other activities in a clinical investigation, necessary for the reconstruction and evaluation of the clinical investigation Note 1 to entry: This includes source data initially recorded in an electronic format.

Abbreviations are defined in Table 26.1-1.

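### Two inductions per configuration place each subject's DFT only in one of at most four energy bands, so the planned mean ± SD depends materially on the step energies and on how the open-ended bands are coded

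*Combined protocol and SAP*

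**What the plan says.** Section 6 sets the aim: "The primary objective of this acute feasibility study is to assess the defibrillation threshold (DFT) when adding a second left parasternal electrode". Section 27.2 defines DFT testing as "Multiple VF conversion tests performed at step-wise energy level to determine the minimum shock energy needed to convert an induced VF episode". For the summary of this primary measure, section 12.1.1 states: "DFTs and shock impedances will be reported as mean ± standard deviation". The same section also plans the conversion percentage at each energy, with a 95% CI.

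On the amount of testing, the synopsis (Investigational Implant Technique and Testing Methodology) gives the first configuration "2 additional VF inductions and shocks per the protocol specified testing sequence" and gives the second configuration two further inductions. Section 11.4 words this as an expectation: "It is expected that testing of each 2-electrode configuration (Parallel and 90°) will require 2 VF inductions". For comparison, section 4.3.1 says of published paired DFT studies: "Such testing would typically require 3 to 5 VF inductions and shocks per test configuration to assess the DFT of each test configuration".

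The Revision C log, used here only as context, describes "a new energy test step sequence that starts at 30 J, rather than 50 J, and requires only 2 VF inductions per shock configuration" and gives the reason: "Current results showed that all subjects were converting at 40 J or lower, so the starting energy was reduced to 30 J". It also records ten complete datasets obtained before that change.

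Under sections 10.3 and 12.2.1, the primary effectiveness set is every Treatment subject, meaning everyone who starts two-electrode testing.

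**The concern.** A subject who converts on both shocks shows only that the threshold is at or below the lower energy tested. A subject who fails both shows only that it is above the higher one. In neither case has a minimum converting energy been found. To compute a mean ± SD, each band must be given a number, and that number is partly a choice of the analyst.

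The study is descriptive, so its summary is its result. Section 8.3 says the study will determine whether the new configuration lowers the energy requirement, and the tertiary objective in section 6 looks at how spacing and angle affect the DFT. Both uses need the low end of the scale to be reported faithfully, and the log's remark about conversion at 40 J or lower suggests that the low bands may be well filled. Section 4.1 quotes a one-electrode DFT of about 37 ± 20 J. A figure printed in the same format invites a direct comparison that the two-shock measurement does not support.

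**Working it through.** **The plan's own figure.** The only computed statistic is the exact 95% CI for 19 of 20 conversions at 50 J. Clopper-Pearson gives a lower limit of Beta(0.025; 19, 2) = 75.13% and an upper limit of 0.975^(1/20) = 99.87%, as stated in section 12.1.1. It describes a conversion percentage. No precision figure is given for the DFT.

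**Number of bands.** k pass/fail shocks have 2^k outcome sequences. Two shocks give 2² = 4, three give 8 and four give 16. The limit of four holds whatever energies Figure 11-1 contains.

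**Size.** The 30 J start comes from the revision log. Everything else here is assumed:
- DFTs are lognormal, with one fixed threshold per subject.
- The second shock is at a lower energy L after success or a higher energy H after failure.
- Each subject is scored at the lowest energy that succeeded.
- Subjects failing both shocks are coded somewhere between H and 80 J.

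For true mean m and SD s, σ² = ln(1 + (s/m)²) and μ = ln m − σ²/2. With m = 20 and s = 11, σ² = ln(1.3025) = 0.264, σ = 0.514 and μ = 2.864. Then P(DFT ≤ x) = Φ((ln x − μ)/σ), which gives 0.138, 0.601, 0.755, 0.852, 0.946 and 0.979 at 10, 20, 25, 30, 40 and 50 J.

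For steps 20/40 J, the bands ≤20, 20–30, 30–40 and >40 J hold 0.601, 0.251, 0.094 and 0.054 of subjects. The reported mean is:
- with double failures coded 40 J: 0.601×20 + 0.251×30 + 0.148×40 = 25.5 J
- with double failures coded 80 J: 0.601×20 + 0.251×30 + 0.094×40 + 0.054×80 = 27.6 J

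| Second steps L/H (J) | In lowest band | Reported mean, double failures coded H to 80 J |
|---|---|---|
| 20/40 | 60% | 25.5 to 27.6 J |
| 20/50 | 60% | 26.9 to 27.6 J |
| 25/40 | 76% | 27.7 to 29.9 J |
| 10/50 | 14% | 30.2 to 30.8 J |

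The same patients, with a true mean of 20 J, are thus reported at about 25.5 to 31 J. Scoring at band midpoints instead gives about 18 to 21 J (true 20 ± 10 J), so the direction of the shift also depends on the coding.

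**SD.** At a true 20 ± 11 J with 20/40 J steps, the reported SD is 7.4 J if double failures are coded 40 J, 11.2 J at 65 J and 14.1 J at 80 J. At a true 10 ± 5 J it is about 2.4 J with 20/40 J steps and about 10 J with 10/50 J steps.

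**Response to a real change.** Halving the true mean from 20 to 10 J (double failures coded H) moves the reported mean from 25.5 to 20.5 J with 20/40 J steps, a fall of 5 J. With 10/50 J steps it moves from 30.2 to 18.2 J, a fall of 12 J. With 20/40 J steps and double failures coded 65 J, a true fall from 37 to 25 J moves it from 42.5 to 31.3 J.

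**Planned percentage per energy.** If the sequence branches, only subjects who passed 30 J receive the lower shock. Among those tested at 20 J, success would be 0.601/0.852 = 71%, against 60% of all subjects.

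**The case against.** Four points weigh on the other side.

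1. Figure 11-1 is not shown and most of sections 11.4.1 to 11.4.5 is redacted. The second steps, a rule for assigning a DFT and any permitted extra shocks may all be there, and section 11.4 says only that two inductions are expected. This stands. A reader might infer that the plan has no assignment rule, but redaction cannot show that. The request is for the rule to appear in section 12.1.1.

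2. A reader might infer that the step energies largely determine the mean, that its SD must be too small, or that it cannot fall below the lowest step. None of these is established. With steps and coding fixed, the mean tracks the true distribution. The SD can be inflated as well as compressed. The floor exists only under lowest-successful-energy coding, which the readable text does not specify.

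3. Section 12.1.1 already plans success percentages at each energy. This helps only in part. Under a branching sequence the lower-energy percentage is conditional on passing 30 J, and mean ± SD remains the stated summary of the primary measure.

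4. The study has no hypothesis, power calculation or planned comparison. Its futility trigger is 40 J, its precision example uses 50 J, and the 37 ± 20 J figure is background. This stands as a limit on the consequences: no sample size or power statement is affected, and separating a true mean of 10 J from 20 J is not a stated goal. It does not make mean ± SD a suitable summary of a four-band result.

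**Conclusion.** The point holds as one about reporting the primary measure. It is exact that two pass/fail shocks resolve a DFT into at most four bands, two of them open-ended. Treating the result as continuous makes the mean ± SD depend materially on step energies and coding.

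The size is illustrative: about 25.5 to 31 J reported for a true mean of 20 J, with 14% to 76% of subjects in the lowest band. It assumes lognormal, fixed thresholds, a 30 J start, the second steps in the table, and lowest-successful-energy coding with double failures coded between the higher step and 80 J. The true steps may lie outside this set.

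The ten earlier complete datasets were obtained under a different sequence, so the four-band limit may not apply to them. Pooling them would mix two measurement grids. A reader might also infer from the 3 to 5 inductions in section 4.3.1 that the testing itself is inadequate. That passage describes typical practice in other studies. It does not show that two inductions are too few for a feasibility study that reports bands.

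**What to change.** Leave the number of inductions and the shock sequence as they are. In sections 7 and 12.1.1:

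- Make the primary effectiveness summary the count and percentage of all Treatment subjects in each DFT band, separately for Parallel and 90°, with exact 95% CIs. Include subjects who fail both shocks, and give those stopped early their own row. As a guide to precision, 12 of 20 in the lowest band (60%) has an exact CI of Beta(0.025; 12, 9) to Beta(0.975; 13, 8), or 36.1% to 80.9%.
- If a mean or median is wanted, use an interval-censored estimate. A subject stopped after one shock then contributes the wider interval that the shock supports.
- Label any simple mean as the mean lowest successful tested energy, and state the coding rule for both open-ended bands beside it.
- Show the ten datasets from the earlier sequence separately.
- State that the result is not directly comparable with the figure of about 37 ± 20 J in section 4.1.

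The cost is some wording, one extra table and a headline figure that looks less precise. No added inductions or subjects are needed.

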11.4.1. S-ICD Implant and Initial Testing

The S-ICD should be implanted according to the system's labeling. [REDACTED]

A series of 15 horizontal black bars of varying lengths, decreasing from top to bottom. Each bar is preceded by a small white gap.

3

A horizontal bar chart consisting of 12 black bars of varying lengths. The bars are arranged in a staggered pattern, with each bar's position relative to the others creating a stepped, staircase-like effect across the frame. The lengths of the bars decrease from left to right, with the shortest bar on the far right.

[REDACTED]

The image consists of a series of horizontal bars of varying lengths and positions. The bars are black on a white background. They are arranged in a staggered, non-overlapping pattern. The lengths of the bars vary significantly, with some being very short and others extending almost to the top and bottom edges of the frame. The positions of the bars are not uniform, creating a sense of depth or a grid-like structure that is partially obscured by the bars themselves. The overall effect is a high-contrast, abstract graphic design.

20. *Using shipping labels provided, return both the used second electrode and the used Investigational S-ICD Y-Adapter to Boston Scientific Product Return department for analysis.

11.4.6. Adverse Event Notification during Acute Clinical Testing in the S-ICD Implant Procedure Visit

If the following adverse events occur during the S-ICD implant and acute testing procedure, they shall be communicated within 24 hours to Boston Scientific clinical study team:

- subject death
- excessive bleeding that requires medication, transfusion, or the use of blood derivatives
- unplanned hemodynamic/cardiovascular support

Boston Scientific Medical Safety will conduct a safety review and may request additional event information to facilitate its review. Boston Scientific shall communicate to all investigators if subject enrollment and implant procedures shall be postponed pending further safety review and will communicate to all investigators when enrollment and implant procedures could resume after the safety review is completed.

11.5. 90-Day Follow-up Visit

